State of the field and current limitations: Previous research on the effects of cannabis on the eyes has been conducted, yet most of this research is decades old and used outdated technology that cannot accurately or frequently measure eye movements and pupil dilation. The literature also presents contradicting results on correlations between cannabis and certain eye movements, specifically regarding nystagmus and smooth pursuit. Despite these studies and the fact that eye movements are currently used in the field to detect drug intoxication, little is known about the causal relationship, if any, between cannabis, eye movements and pupil dilation. To date, no published studies have used modern VR eye trackers and data analysis to build a predictive model of cannabis intoxication. The current study seeks to explore the effects of cannabis on eye movements using a sophisticated eye tracking software to provide an objective, accurate measure of cannabis impairment.

Specific Aims and Hypotheses

Aim 1: Examine the relationship between cannabis intoxication and eye behavior.

Hypotheses: (a) Active cannabis (7% THC) will have an effect on eye behavior, evidenced by lack of convergence, lack of smooth pursuit, presence of nystagmus and pupil dilation when compared to inactive placebo cannabis (0% THC).

Exploratory Aim: Examine the relationship between experimental pain and pupil size.

Hypotheses: (a) Changes in pupil size will correlate with subjective reports of experimental pain threshold and tolerance using Quantitative Sensory Testing thermal pain.

Inclusion/Exclusion Criteria

Description of Subject Population:
Non-treatment seeking cannabis smokers.

CRITERION	METHOD OF ASCERTAINMENT
Inclusion:	
1. Males/non-pregnant females aged 21-55 years	Age verified via identification/Non-pregnancy confirmed via urine toxicology
2. Report smoking cannabis \geq 1 day per week, and \geq 1 joint (~0.5 grams) per smoking day, during the 4 weeks prior to screening	Self-report during clinical interview
3. Urine test positive for recent cannabis use	Urine toxicology
4. Body Mass Index from 18.5-34 kg/m ²	Physical examination
5. Not currently seeking treatment for their cannabis use	Self-report during clinical interview
6. Able to perform all study procedures (i.e., does not experience discomfort or nausea from VR headset, can perform computer tasks)	Training session

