7. For women, not pregnant, lactating, or breast-feeding and currently practicing an effective form of birth control (double-barrier methods, hormonal birth control pills, hormonal implants, or IUDs)	Self-report during clinical interview, blood, and urine pregnancy test (7091R), physical examination
Exclusion:	
1. Meeting the DSM-V criteria for Severe Cannabis Use Disorder or any other Use Disorder other than for Cannabis, Nicotine, or Caffeine; any other psychiatric disorder	Clinical interview
2. Report using other illicit drugs \geq 1 day/week in the prior 4 weeks; positive for anything other than THC > 1x during screening	Clinical interview, urine toxicology
3. Abnormality with the eyes which may affect the eye tracking technology such	Physical examination, training/calibration session with VR eye-tracking device

as color blindness, naturally occurring nystagmus, amblyopia, strabismus, age-related macular degeneration (AMD), cataract, diabetic eye disease, glaucoma, dry eye, extreme refractive error, bacterial or viral infections of the eye.	
4. If medical history, physical and psychiatric examination, or laboratory tests performed during the screening process revealed any significant illness (e.g., diabetes, cardiovascular disease, hypertension (BP >140/90), hepatitis, clinically significant laboratory abnormalities, chronic obstructive pulmonary disease, Parkinson's disease, dementia, cognitive impairment, history of a seizure disorder, history of traumatic brain injury, any immunocompromising conditions such as HIV/AIDS, cancer, or diabetes, or LFTs > 3x upper limit of normal)	Medical history, physical examination, laboratory tests, ECG
5. Current licit use of medical cannabis	Self-report, physical examination
6. Current pain	Self-report during clinical interview, physical examination, medical history
7. User of supplemental oxygen	Medical history, physical examination

Study Procedures

General Overview

This study will examine the effects of cannabis intoxication on eye behavior. Eleven eye-task batteries will be conducted with a VR HTC Vive with Pupil Labs Eye Tracking headset. Healthy cannabis users (N=30, 15M, 15F) will complete a training session followed by two counterbalanced outpatient laboratory sessions in a randomized, double-blind, placebo-controlled (0% vs. 7% THC) design.

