In order to collect exploratory data on the potential utility of pupil dilation as a biomarker of pain response, participants will undergo Quantitative Sensory Testing (QST) to induce cold pain threshold and tolerance latencies. We will conduct this assessment during training rather than within the laboratory sessions to avoid the potential confound this task may have on measuring cannabis' effects on eye-tracking and pupil dilation. Further, cannabis administration would also affect our ability to detect changes in pupil dilation as a result of exclusively experimental pain induction. For QST, a thermal testing analyzer (Medoc TSA-II NeuroSensory Analyzer) with a 30 x 30 mm Peltier thermode is used to apply a cold stimulus on the thenar eminence of the palm. The temperature is set to 4.0°C. Using a computerized response button, participants will note the time (in seconds) at which they begin to perceive the cold as painful, and when it becomes too painful to continue. At this latter point, the program will discontinue the cold stimulus and return to baseline temperature. They will also continuously rate the magnitude of perceived pain using a computerized VAS (Co-VAS, 0-100) throughout stimulation. Throughout this assessment, changes in pupil dilation will be measured using the eye-tracking headset and correlated to their subjective Co-VAS pain responses. If participants exceed the 3-minute cut-off, the task will be discontinued in order to avoid tissue damage.

We will also describe the paced-puff procedure of cannabis administration (Foltin et al., 1987) during the training session. We will inform participants that during the two laboratory sessions, we will be directing them through smoking a cannabis cigarette, and that we do this in attempt to standardize the amount of cannabis that each person is getting. We will inform them that this procedure "involves cues to prepare to inhale (5 sec), inhale (5 sec), hold the inhalation (10 sec), and exhale, with 40 seconds in between each puff". Participants will smoke two-thirds of the cigarette using this procedure.

Laboratory Sessions:

There will be two counterbalanced, within-subjects laboratory sessions, which can occur with no wash-out period in between if scheduling permits. Participants will abstain from alcohol and cannabis use 15 hours prior to each laboratory session.

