- Horizontal Gaze Nystagmus (HGN): The stimulus (a fixation cross) moves from the center of the visual field to 45 visual degrees to the right and left and is held at each extreme for 10 seconds.
- Vertical Gaze Nystagmus (VGN): The stimulus (a fixation cross) moves from the center of the visual field to 40 visual degrees up and down and is held at each extreme for 10 seconds.

2. Smooth Pursuit (SP): The stimulus (a fixation cross) moves from each extreme of the visual field at a speed of 40 degrees/second. This test measures the tracking ability of the eyes. The smooth pursuit test is embedded in the nystagmus tests; it takes place in between the HGN/VGN tests as the stimulus moves from the horizontal/vertical extremes. Horizontal smooth pursuit is assessed as the stimulus moves from one side of the visual field to the other, while vertical smooth pursuit is assessed when the stimulus moves from the upper extreme of the visual field to the lower extreme, or vice versa.

2. Convergence: The stimulus (a fixation cross) moves from 12 inches to 2 inches away from the participant's nose at a continuous speed over 5 seconds, then is held at that point for 10 seconds.

3. Pupil response: For both pupil tests, participants are asked to stare directly at the stimulus (a large grey fixation cross) to minimize eye movement.

- Pupillary Light Reflex (PLR): Bright light is presented in a previously dark setting for 10 seconds followed by 30 seconds of no light for pupil adjustment.
- Pupillary Light Flash Reflex (PLFR): Light is flashed once for one second followed by an observation period of 5 seconds. During the observation period, no lights flash and the participant's reaction to darkness is assessed.

Tests conducted:

Test	Time (sec)
Horizontal Smooth Pursuit x 4	9.2
HGN Hold x 4	40
Vertical Smooth Pursuit x 4	9.2
VGN Hold x 4	40
Convergence In x 3	4.89
Convergence x 3	30
Darkness	30
PLR – Both Eyes	10
Darkness	30
PLR – Right Eye	5
Darkness	30
PLR – Left Eye	5
Darkness	15

PLFR	1
Darkness (observation)	5
Total time:	264.29 sec/ 4.40 min

Session Time		Study procedures and assessments
TIME (hours)	Cannabis admin (mins)	
0900	-60	Participant arrives
0915	-45	Urine, vitals (BP and HR), breath CO and EtOH, TLFB, breakfast
0930	-30	Baseline assessment: Subjective-effects Battery (SEB), Eye-tracking Battery (ETB)
1000	0	Cannabis administration: (7% or 0%)
1000	0	Post-cannabis 1: SEB, ETB, vitals

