Bloodwork to determine eligibility and pregnancy status for this study is conducted under screening protocol #7091R, prior to any screening or study procedures for this study.

Assessment Instruments

Screening Assessments (conducted under #7091R):

- 1) Telephone Interview: 20min
- 2) Structured Clinical Interview for DSM-5: variable; relevant sections are performed if participant endorses any of the SCID screening instrument questions
- 3) Timeline Follow-Back interview for substance use: 10min
- 4) Beck Depression Inventory: 5min
- 5) General Health Questionnaire: 5min
- 6) The Short Form Health Survey: 5min
- 7) Medical History Questionnaire: 5min
- 8) General Pain Index Questionnaire: 5min
- 9) 12-lead electrocardiogram: 15min
- 10) Blood count with differential, chemistry profile, liver enzymes, and GGTP
- 11) Urinalysis with 12-panel urine drug testing
- 12) Physical and Psychiatric Examination: 30min

Behavioral Performance Tasks during Sessions:

- 1) Quantitative Sensory Testing thermal pain (QST-TP; at training session only): Using a thermal testing analyzer (Medoc TSA-II NeuroSensory Analyzer) with a 30 x 30 mm Peltier thermode is used to apply a cold stimulus on the thenar eminence of the palm. 5 min

2) ETB (Eye Test Battery): Participants will complete four eye tracking tasks in a VR environment. Participants will follow a target with their eyes as it moves up, down, left, right, forwards, and backwards. 5 min.

3) SEB-VAS (Subjective Effects Battery-Visual Analogue Scale): Participants will rate the extent to which they are experiencing 44 different positive (e.g., 'Mellow') and negative (e.g., 'Anxious') mood states, physical symptoms (e.g., 'Muscle Pain') and drug effects (e.g., 'High') at that moment: 2min

Physiological Measures during Laboratory Sessions:

- 1) Quantitative Urinalysis: Samples analyzed daily
- 2) Heart Rate and Blood Pressure: 1min
- 3) Carbon monoxide expiration: 30 sec
- 4) Breath alcohol concentration: 30 sec

Research Related Delay to Treatment

Research procedures will not result in a delay to treatment since participants are not seeking treatment for cannabis use. Nonetheless, all will be informed of cannabis treatment at STARS in case they change their minds in the future.

Clinical Treatment Alternatives

Participants are not seeking treatment. The alternative is to not participate in this study.

Risks/Discomforts/Inconveniences

Medications:

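### The pain–pupil test is done at a training visit that the abstinence rule and recent-use checks do not cover

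*Combined protocol and SAP*

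**What the plan says.** **Where the pain test sits.** The list of behavioural tasks in Assessment Instruments places it at one visit: "Quantitative Sensory Testing thermal pain (QST-TP; at training session only". The section on Training Session 1 gives two reasons. The first protects the main aim: "We will conduct this assessment during training rather than within the laboratory sessions to avoid the potential confound this task may have on measuring" the effects of cannabis on the eyes. The second protects the pain data: "cannabis administration would also affect our ability to detect changes in pupil dilation as a result of exclusively experimental pain induction".

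**Training is not a laboratory session.** In the General Overview, participants "will complete a training session followed by two counterbalanced outpatient laboratory sessions".

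**Where the controls sit.** The abstinence rule stands under Laboratory Sessions: "Participants will abstain from alcohol and cannabis use 15 hours prior to each laboratory session". The timetable for those sessions has, 45 minutes before smoking, "Urine, vitals (BP and HR), breath CO and EtOH, TLFB, breakfast". Assessment Instruments lists urinalysis, heart rate and blood pressure, CO and breath alcohol under "Physiological Measures during Laboratory Sessions". The training description covers headset adaptation, the pain test and an account of the smoking procedure. It mentions no abstinence, breath test or report of recent use.

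**Who is tested.** Participants smoke on at least one day a week, and the inclusion criteria require "Urine test positive for recent cannabis use". No maximum frequency is set.

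**The concern.** The protocol gives cannabis interference as one reason for keeping the pain test away from the smoking sessions, but nothing in the plan keeps participants' own use away from the visit chosen instead. Someone who smoked or drank shortly before training could be tested without any departure from the plan.

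The protocol itself gives grounds for care. Its main hypothesis includes pupil dilation under active cannabis, and the background says the pupil's light reaction tends to be slow in the first hours after use. The pain test is not repeated and has no randomised comparison. If recent use differs between participants and is not recorded, the analyst can neither adjust for it nor run a sensitivity analysis. At stake is the interpretation of the exploratory aim. The cannabis comparison in Aim 1 uses only the laboratory sessions, where the controls apply.

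**Working it through.** The plan gives no power, error rate or planned precision for the pain–pupil correlation, so there is no figure to reproduce. The check has three parts.

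**1. Scope of each control**

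| Control | Laboratory sessions | Training session |
|---|---|---|
| 15-hour abstinence from alcohol and cannabis | Stated | Not stated |
| Breath CO and breath alcohol | Timetable and Assessment Instruments | Not stated |
| TLFB | Timetable | Not stated (done at screening) |
| Pain test | Not done | Done |

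The pain test is done at the one session type that has none of these controls. Screening urine toxicology and TLFB describe use before entry, not the participant's state at a later visit.

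**2. Which analyses are exposed**

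Two analyses are described. The Lay Summary and the exploratory hypothesis relate pupil change to pain threshold and tolerance, which give one value of each per person, so that correlation compares people. Recent use that alters pupil reactivity in some participants adds unexplained variation. If it also alters pain reports, it biases the correlation.

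The training section correlates pupil change with a continuous pain rating. If this is done within each person, a constant shift in pupil size drops out. Only a change in pupil reactivity would remain.

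**3. How many might be affected (illustration)**

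Inputs:
- N = 30 (General Overview).
- Psychoactive effects last 3–4 hours (Current Research); the upper end, 4 hours, is used.
- Minimum use is one day a week (Inclusion/Exclusion Criteria).
- Assumptions: training falls at a random time relative to last use, and every participant smokes once per interval. One interval per week and one per day are taken as the two ends of the range.

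Formula: expected number = N × (window ÷ interval between uses).

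- Once a week: 30 × 4/168 = 30 × 0.024 = 0.7.
- Once a day: 30 × 4/24 = 30 × 0.167 = 5.0.

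That is about 1 to 5 of 30. The same formula with the 15-hour abstinence period gives 30 × 15/168 = 2.7 and 30 × 15/24 = 18.8.

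**The case against.** The case on the other side has real force.

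- **Motive.** The first stated reason for the placement is to keep pain out of the cannabis measurements, and the placement achieves that. The second is worded about giving cannabis in the study, not background use. A reader might infer that the test was moved solely to keep cannabis out of the pupil signal; the text does not say so. What remains is that the protocol explicitly regards cannabis as a threat to reading pain-related pupil change, and its reasoning applies equally to a participant's own recent use.
- **Consequence.** A reader might infer that the aim can no longer attribute any pupil change to pain. That goes too far. A within-person analysis is partly protected. Bias between people also requires cannabis to alter pain reports, which the protocol does not discuss. The background calls the pupil findings controversial, although it says most research shows some relationship with dilation.
- **Records.** TLFB is taken again at each laboratory session and may reach back to the training date. Its look-back period and hour-level detail are not given, so it may recover recent use only in part. The consent pages were not available and may carry an instruction for training.
- **Size.** A reader might take the 15-hour result, about 3 to 19 people, as the number affected. The protocol does not say that pupil effects last 15 hours, so the 4-hour result is the relevant one. Severe Cannabis Use Disorder is excluded, which partly restrains heavy use but does not cap frequency.
- **Importance.** The aim is exploratory and the data are called preliminary. That lowers the priority but does not remove a gap that is cheap to close.

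**Conclusion.** The point holds in a limited form. As written, the abstinence rule and the breath and TLFB checks cover the two laboratory sessions and not the training session, where all the pain data are collected. Participants could therefore be tested after recent cannabis or alcohol use. The documents do not show that anyone would be.

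The likely effect is noise and possible bias in an exploratory correlation, greatest for threshold and tolerance. The range of about 1 to 5 of 30 illustrates scale. It is not an estimate: it depends on random timing and uniform smoking frequency, and it would rise with use more often than daily.

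A separate inconsistency bears directly on the same data. The Medications paragraph under Risks/Discomforts/Inconveniences says active cannabis is given at the training session as well as at one laboratory session. The training section says only that the smoking procedure will be described there. If cannabis were given at training, its order relative to the pain test would matter, and no explicit order is stated. Extending the abstinence rule would not settle this.

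**What to change.** 1. Extend the abstinence sentence under Laboratory Sessions so that it also covers the training session.
2. Before the pain test, record the time of last cannabis and last alcohol use by TLFB or self-report, and run the breath CO and breath alcohol tests already used at laboratory sessions. CO does not distinguish cannabis from tobacco smoke, and nicotine use disorder is not an exclusion, so CO should support the use report rather than replace it.
3. Where use inside the abstinence period is found, reschedule the pain test or flag that participant's pain data. State in advance that the pain–pupil correlations will be reported with and without flagged participants.
4. Reconcile the Medications paragraph with the training section on whether cannabis is given at training and, if so, in what order relative to the pain test.

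The cost is small. Assessment Instruments gives 30 seconds for each breath test and 10 minutes for TLFB, and no new instrument is needed. The downside is an occasional rescheduled training visit or a few flagged participants. The laboratory sessions and Aim 1 do not change.

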In each session, the participant will smoke two-thirds of one cannabis cigarette according to our paced-puff procedure (Foltin et al. 1987). They will complete an eye task battery (5 minutes per battery) 15 minutes prior to smoking as a baseline measure in each session, and again at the following timepoints: 0, 15, 30, 45, 60, 75, 90, 105, 120, and 165 minutes post-cannabis. Baseline assessments will be compared to those at post-cannabis timepoints.

In order to collect exploratory data, we will also conduct one pain assessment during the training session (described below).

Screening:

Initial telephone interviews will be carried out by research assistants who have been trained by [name], during which time potential participants will be asked about their current and past drug use and general health. To conduct this telephone interview, we are requesting a waiver of consent.

After initial determinations of eligibility over the phone, volunteers will come into the Cannabis Laboratory for two screening visits. At the first screening visit, they will be asked to sign our currently approved outpatient screening consent form (#7091R), allowing us to collect questionnaire data, conduct interviews, obtain medical information including a medical history and bloodwork (including blood pregnancy test for women at screening), and do an ECG. Potential participants will be told that they will be taking part in a study investigating the effects of smoked cannabis and eye movements. After the general screening process, a study psychologist ([name], [name], [name]) will explain the details of the study procedure and confirm that the volunteer understands what participation entails, after which they will sign the study-specific consent form (#7844).

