At the second screening visit, conducted under the study-specific consent form (#7844), study physicians will then conduct a medical exam that includes a physical exam and a psychiatric evaluation (if needed), review medical results, and review study inclusion/exclusion criteria. At screening, the study physician and study PI will explain that the cannabis in this study could be harmful to a developing fetus or young infant, and we will confirm via self-report that women are using and will continue to use a birth control method (double-barrier protection, hormonal birth control pills, hormonal implants, or IUDs) and are not breast-feeding while in the study. The study physician will also explain that birth control methods must be used properly and consistently in order to most effectively avoid pregnancy, that even still they could become pregnant, and thus they should inform research staff immediately if they think they might be pregnant. If a participant becomes pregnant during study participation, they will be discontinued from the study, and we will provide referrals for obstetrical follow-up.

Both screening sessions will be conducted in the Cannabis Laboratory of the Substance Use Research Center (SURC), located on the 3rd floor of the NYS Psychiatric Institute.

Laboratory Facility:

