1015	15	Post-cannabis 2: SEB, ETB, vitals
1030	30	Post-cannabis 3: SEB, ETB, vitals
1045	45	Post-cannabis 4: SEB, ETB, vitals
1100	60	Post-cannabis 5: SEB, ETB, vitals
1115	75	Post-cannabis 6: SEB, ETB, vitals
1130	90	Post-cannabis 7: SEB, ETB, vitals
1145	105	Post-cannabis 8: SEB, ETB, vitals
1200	120	Post-cannabis 9: SEB, ETB, vitals
1245	165	Post-cannabis 10: SEB, ETB, vitals
1300	180	Field sobriety test, vitals, MMSE, discharge

The total time for each trial, including calibration, the eye tracking battery, and the subjective-effects battery is approximately 10 minutes.

At 180 minutes after cannabis administration participants will complete field sobriety tests, vital signs, and a Mini-Mental State exam, and will be permitted to leave once they meet discharge criteria. Criteria for discharge will be met when participants report no ongoing subjective drug effects and have no signs of impairment or intoxication, pass the field sobriety test, have normal vitals, and a normal mental status score as assessed by the Mini-Mental State Exam (MMSE). [name], [name], or a study physician will make the final determination that the patient is sober and medically stable and can leave the facility. In the rare event the participant is still impaired they will be paid an extra \$10 for every hour they stay. They will be instructed not to drive a car after administration of cannabis; therefore, participants will be required to take public transportation (i.e., bus or subway) both to and from the laboratory each session, for which they will be reimbursed.

Video recordings of the eyes will be taken using Pupil Labs at each timepoint during both sessions. These videos will make calibration more accurate; research staff will be able to confirm correct pupil calibration after the session is complete. These videos will be available only to research staff (investigators and assistants), will not be used for educational purposes, and will be deidentified and stored by patient study identification number on an encrypted computer in the Cannabis Laboratory. We will destroy these videos at the conclusion of data analysis (approximately 3 years after study initiation).

Criteria for Early Discontinuation

If a woman becomes pregnant during study participation (confirmed via urine pregnancy test), her participation in the study will be discontinued.

Blood and other Biological Samples

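### In the visible text, pregnancy testing is scheduled only at screening, and no negative result is required before cannabis at either laboratory session (minor, cheap to close)

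*Combined protocol and SAP*

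**What the plan says.** **At screening.** Inclusion criterion 1 confirms non-pregnancy through urine. Criterion 7 relies on self-report, blood and urine pregnancy tests tied to protocol 7091R, and a physical examination, and also requires effective contraception. The Screening section describes the first-visit bloodwork as "including blood pregnancy test for women at screening". Under Blood and other Biological Samples, "Bloodwork to determine eligibility and pregnancy status for this study is conducted under screening protocol #7091R", and this is placed ahead of any procedure of the present study.

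**After screening.** The Screening section tells women that "they should inform research staff immediately if they think they might be pregnant". Criteria for Early Discontinuation says: "If a woman becomes pregnant during study participation (confirmed via urine pregnancy test), her participation in the study will be discontinued".

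**On the laboratory day.** The 0915 row of the session timetable lists "Urine, vitals (BP and HR), breath CO and EtOH, TLFB, breakfast". Smoking is at 1000. Under Physiological Measures during Laboratory Sessions, the urine entry is "Quantitative Urinalysis: Samples analyzed daily".

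**On the hazard.** The Screening section says that "the cannabis in this study could be harmful to a developing fetus or young infant", and the Risks section lists adverse pregnancy outcomes linked to cannabis use.

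**The concern.** The protocol excludes pregnant women because it regards the study drug as a hazard to a fetus, so the status that matters is the status at dosing. Between the screening tests and the last dose come a training session and two laboratory sessions, and no maximum interval is stated. Over that time the written safeguards are contraception, confirmed by self-report, and the request to tell staff of a suspected pregnancy. Neither detects a pregnancy that the woman has not noticed. Staff who followed the visible text exactly could give her active cannabis while a urine sample taken that morning went untested for pregnancy. What is at stake is participant safety; the estimates, power and blinding are not touched.

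**Working it through.** The plan states no figure to reproduce. The check is a reading of every place that mentions pregnancy, urine or pre-session procedures, followed by a count.

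**Step 1: each test, with its timing and its effect on dosing.**
- Criteria 1 and 7, the Screening section and the 7091R bloodwork: tests made to establish eligibility. No repeat is stated.
- Criteria for Early Discontinuation: a urine pregnancy test during the study, with a stated purpose (confirming a pregnancy). No time, no trigger and no link to dosing.
- Timetable, 0915: urine is collected. The breath assays are named; the urine assay is not.
- Session measures: urinalysis, with samples analysed daily. That wording does not require a result before 1000 and names no pregnancy test.
- Procedures for minimizing risks: pregnancy is covered by ineligibility and by discontinuation with referral. Session-day testing is not mentioned.

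No visible text makes dosing conditional on a negative test.

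**Step 2: how far the silence can be pressed.** The list of screening assessments under 7091R gives "Urinalysis with 12-panel urine drug testing" and also leaves out the pregnancy test, although criterion 7 says one is done under 7091R. Omission from a list in this protocol is therefore weak evidence that a test is not run. The difference is that other sections supply the missing screening test, while no visible section supplies one for the laboratory sessions.

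**Step 3: counts.** Inputs, from General Overview: 30 participants, 15 of them women; two sessions each, one active and one placebo; two-thirds of a cigarette per session. All are assumed to complete.
- Active administrations to women: 15 × 1 = 15.
- All administrations to women: 15 × 2 = 30, of 30 × 2 = 60 in the trial.
- Active exposure per woman: two-thirds of one cigarette.
- Time from urine collection to smoking: 1000 − 0915 = 45 minutes.

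These are counts of administrations, not of expected pregnancies.

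**Step 4: scale, on assumed inputs only.** The documents give neither a pregnancy rate nor the interval from screening to the sessions. Let r be an assumed annual pregnancy rate under contraception and w an assumed number of weeks from the screening test to the last session. The chance that at least one of 15 women conceives in that interval is 1 − (1 − r)^(15w/52):
- r = 1%, w = 1: 0.3%
- r = 5%, w = 4: 5.7%
- r = 10%, w = 8: 21.6%

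The result moves from negligible to appreciable with the assumptions, so it supports no point estimate. It also overstates what a session test would add: some women would report a pregnancy themselves, and a very recent conception would not yet show on a strip.

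**The case against.** The strongest reply is that the site probably tests already. The discontinuation section names a urine pregnancy test during participation and does not tie it to self-report. The only in-study urine collection shown is the 0915 sample. Criterion 1 uses a general urine label to cover a pregnancy check, so the unspecified 0915 entry may well do the same. Protocol 7091R and the consent pages are not in the file and might specify a session test. All of this stands, and it rules out the stronger reading that women are dosed untested: the documents do not show that. What survives is narrower. None of these texts requires a negative result before 1000.

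It would also be tempting to say that every pregnancy test with a stated purpose belongs to screening. The discontinuation section contradicts that; only the scheduled testing is confined to screening.

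A further reply is that 30 administrations overstates the exposure, because half are placebo with 0% THC. That is right. The relevant count is 15, in women who by inclusion criterion already smoke at least one joint on at least one day a week. The 30 matters only for the number of strips.

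**Conclusion.** The point holds in a limited form and is minor. The visible text schedules pregnancy testing only at screening, relies on self-report afterwards, and does not make either laboratory dose depend on a negative result. The exposure concerned is 15 active administrations to women, each two-thirds of a cigarette, if all 15 complete. The added risk is small because entry tests and contraception are required, participants already use cannabis, and the two sessions may follow each other without a wash-out. This rests on the text available here; a session test written into 7091R or the consent form would reduce the point to recording it in the protocol.

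A separate inconsistency should be resolved. The Risks section says that 7% THC is given at the training session. The training section only describes the puff procedure and places smoking in the two laboratory sessions. A reader might infer 15 further active doses to women at training. The fuller procedural text does not support that, so none is counted.

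**What to change.** In the 0915 timetable row and in the session measures, state that women's urine is tested for pregnancy and that a negative result is required before the 1000 administration. Apply this at both sessions: the study is double-blind, so staff cannot restrict it to the active day. If the site already tests, one line recording the practice is enough.

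The cost is one or two lines of text, about 15 × 2 = 30 test strips on urine already collected (none extra if it is already tested), and an occasional cancelled session.

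Separately, align the Risks statement about training with the training-session section. If a training dose is in fact intended, the same pre-dose test should apply there.
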